This study will use a single group repeated-measures design to address the following Specific Aims:

Aim #1: To determine the feasibility of a 6-week UZIT intervention in community-dwelling adults with PH. Feasibility will be determined by 1) recruitment rate (>40% recruited from those approached), 2) enrollment (\geq two participants /month) (Carter et al., 2013; Uebelacker et al., 2010), 3) home practice (\geq 1/week), and 4) retention rate (\geq 70% of participants remaining at study completion). We will also explore UZIT interventionists' perception about study feasibility.

Hypothesis 1: UZIT will meet feasibility targets for community-dwelling adults with PH.

Aim #2: To determine the acceptability of UZIT among community-dwelling adults with PH for symptom management. Acceptability will be determined by participants' evaluation of the UZIT program (composite mean System Usability Scale score > 5, scale 1-7), (Brooke, 1986) and session completion rate (at least 5 of 6 sessions [83% attendance]) (Campo et al., 2013; Cohen et al., 2007; Lee et al., 2010; Lengacher et al., 2011; Palumbo, Wu, Shaner-McRae, Rambur, & McIntosh, 2012) by the participants retained at the study end. An exploratory sub-aim (Aim 2-A) is to determine what components of the UZIT program are preferred by adults with PH. We will also explore UZIT interventionists' perception about participants' acceptability of the UZIT intervention.

Hypothesis 2: UZIT will meet acceptability standards among community-dwelling adults with PH.

Aim #3: To explore the preliminary efficacy of UZIT intervention.

Aim #3a: To explore the preliminary efficacy of weekly UZIT sessions on dyspnea, pain, fatigue and anxiety.

Aim #3b: To explore the preliminary efficacy of a 6-week UZIT program on PH-related symptoms and HrQoL.

Hypothesis 3a: Patients will report reduced presence and intensity of dyspnea, pain, fatigue and anxiety after each UZIT session.

Hypothesis 3b: Patients will report a decrease in the presence, severity, and activity interference for PH-related symptoms and improvement in HrQoL after UZIT program compared to baseline.

III. Background and Rationale

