This is an important foundational study to establish feasibility and acceptability and, potentially, to identify needed refinements, in integrative therapies for symptom management in complex chronic, life-limiting cardio-pulmonary disease. Once UZIT is established as feasible and acceptable for PH patients, future research will focus on testing the efficacy and effectiveness of UZIT to reduce symptom burden and promote HRQOL for persons with complex chronic, life-limiting cardio-pulmonary disease. Additional studies will include analysis of cost and health care utilization outcomes. The long-term goal of this program of research is to advance knowledge and evidence-based application of integrative therapies to manage symptoms and promote quality of life for persons with complex chronic, life-limiting cardiopulmonary conditions.

III. Procedures

A. Research Design

This feasibility and acceptability study will use a pre/post intervention (6-weeks UZIT program) mixed-method design with repeated (weekly) measures of a single cohort of patients with PH. We will also explore preliminary efficacy testing to construct sample size estimates for future randomized control trials. Patients will serve as their controls.

B. Sample

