The primary purposes of this study are to establish feasibility and acceptability of the UZIT intervention. A descriptive analysis will be applied. Pilot feasibility and acceptability studies of integrative behavioral approaches similar to the one proposed here generally include 6-19 participants (Cohen et al., 2007; Freedenberg, Thomas, & Friedmann, 2015; Lengacher et al., 2011; Palumbo, Wu, Shaner-McRae, Rambur, & McIntosh, 2012; Uebelacker et al., 2010; Yeh et al., 2010). With regards to preliminary efficacy outcomes of PH-related symptoms and PH-related HRQoL, we estimated statistical power. Power analysis using two-sided paired tests (*t*-tests for continuous and McNemar test for dichotomous/categorical outcomes) indicates that a sample size of 15 has sufficient power (≥ 0.8) to detect large effect size (standardized mean difference of 0.78 or greater for continuous outcomes; odds ratio of 7 or greater for dichotomous/categorical outcomes, assuming that proportion of discordant pairs is 0.6) with a significance level of 0.05. Therefore, small to medium effect sizes will not be detected as statistically significant in this study. As a pilot study to generate information on preliminary efficacy, we will not rely on statistical significance, but rather on clinical differences. Anticipating 10-15% attrition rate over a 6-8 week behavioral intervention study (Carter et al., 2013; Grossman et al., 2010), we will enroll 20 participants to achieve a final minimum sample of 15.

C. Measurement / Instrumentation

Table 1 outlines the data collection timeline. Participants will provide demographic data at enrollment. The PI's preliminary work demonstrated that PH patients were able to complete four questionnaires in outpatient clinic settings within 15-minutes without undue burden. One hundred and eleven participants of 115 enrolled (96.5%) completed all four questionnaires without difficulty.

Table 1: Data Collection Timeline

Measurement	Study AIMS	Week 0	Week 1	Week 2	Week 3	Week 4	Week 5	Week 6
Consent		X						
Demographics		X						
UZIT Intervention			X	X	X	X	X	X
Phone Call			X	X	X	X	X	X
Diary Record	2, 3b		X	X	X	X	X	X
Field Notes	2		X	X	X	X	X	X
Debriefing (P)	2				X			X
Debriefing (I)	2, F		X	X		X	X	
Session Video Recording	2, F		X	X	X	X	X	X
Acceptability Survey	2							X
PAHSS	3b		X					X
Dyspnea, Pain, Fatigue, Anxiety	3a		X	X	X	X	X	X
Manipulation Check	F						X	
Enactment Check	F						X	
CAMPHOR	3b		X					X

Data Collection Instruments

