The UZIT Interventionists questionnaire will also solicit interventionists' perception about UZIT feasibility, patients' acceptability of UZIT intervention, and UZIT fidelity. Because interventionists had been closely involved in the creation and refinement of the UZIT intervention protocol and fidelity training throughout the course of study period, series of questions in this questionnaire will include these 3 aspects of query (please see attached). Interventionists' audio recorded comments will be transcribed verbatim, coded and categorized for common themes using NVivo qualitative data analysis program.

D. Detailed study procedures

Intervention.

Individual, one-to-one UZIT sessions will be delivered by experienced therapists who are trained and certified in UZIT curriculum and training protocol (4 months coursework + 6-8 hours/week practice+50 hours clinical practicum). Individual rather than group intervention delivery reduces distractions and the social influences of a peer group. Private UZIT sessions are also more conducive to tailored treatment and allow for a more accurate symptoms query. A competency check-off list will be required of all UZIT interventionists before delivering study intervention. At least two experienced, UZIT-trained therapists will be trained in the study intervention delivery according to the research protocol. Sessions will be arranged at a convenient time for patient and therapist and conducted at the OSU Integrative Medicine outpatient facility in Columbus, Ohio. The facility is easily accessible and conveniently located close to the main medical facility; parking is free. Patients will participate in a total of 6 visits lasting approximately 1 to 1.5 hours per visit to be scheduled within an 8-week period. Participants will receive an incentive of \$30.00 in gift certificates for the entire study, distributed in \$5 increments at the end of each visit. This amount is considered reasonable because the study intervention (personal UZIT sessions) has an estimated market value of \$100.00 per session and will be provided at no cost to participants.

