The primary threat to internal validity is intervention fidelity which is a major concern in behavioral intervention research using multi-component mind-body integrative. As previously described, we identified specific ways to ensure intervention dose, intervention delivery, intervention receipt, and intervention enactment to avoid study bias. Study interventionists will be trained according to the intervention protocol and their competency will be checked at the initiation of the study as well as throughout the study period. Their delivery method and dose will be checked against a pre-defined fidelity checks through video recording review. Post-UZIT session debriefing with interventionists will provide an on-going quality assurance check

making sure that there is no drift in study implementation procedure. Intervention receipt and enactment will be checked by using manipulation checks and enactment checks questions.

E. Data Analysis

Descriptive statistics (mean and standard deviation (SD) for continuous variables and frequency and percentage for categorical variables) will be used to describe relevant demographics and clinical characteristics of the sample such as sex, gender, NYHA classification, and education level.

Aim 1: To determine the feasibility of a 6-week UZIT intervention in community-dwelling adults with PH.

Feasibility will be evaluated by recruitment and retention rates. Recruitment rate will be determined by 1) proportion of patients approached who consent to the study, and 2) length of time (months) required to recruit 20 subjects. Retention rate will be calculated as the proportion (completed/enrolled) of participants remaining to study completion. UZIT Session Video Recording: In addition to fidelity monitoring of initial 30 recordings, subsequent 30 recordings (total of 60 or 50%) will be randomly selected for quality/intervention fidelity audit using a checklist tool with the expected 80% protocol adherence level.

Aim 2: To determine the acceptability of UZIT among community-dwelling adults with PH for symptom management. Sub-aim (2A): to determine what components of the UZIT program are preferred by adults with PH.

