Acceptability: Acceptability scores will be calculated from participants' responses to the SUS. Composite means and standard deviations will be computed for each item. An average of the total SUS scores for the sample (mean, SD) will be calculated. Field Notes: Semi-structured observation notes with free-text narrative will be transcribed, coded, formatted, and refined into qualitative themes regarding participant perceptions of the therapy, their practice of UZIT components, and symptom experience. Patients' preference rating of each UZIT component will be tabulated. UZIT Attendance: We will compute the number of sessions attended and completed per participant and for the total sample by range, median, mean and mean proportion. Home Practice Diary: Participants' written responses to questions on strategies for symptom self-management will be transcribed, coded, formatted, and refined into qualitative themes using basic qualitative description.(Miles, Miles, A Michael Matthew B, & Huberman, 1994). We will review the first participant's diary, develop a coding list and definitions, review and discuss with Sponsor in weekly analytic sessions using the constant comparison of subsequent diary entries. A stem-leaf diagram will be used to identify common themes. Participants' daily symptom ratings, the length of UZIT home practice time (minutes/day) will be analyzed descriptively (range, mean, SD, median, mode). Although self-reported health diary data collection method has potential limitations such as inaccurate and/or incomplete data (L. E. Burke et al., 2008; Stone, Shiffman, Schwartz, Broderick, & Hufford, 2003), it is suitable for use in this limited budget research proposal for the following reasons: ease of transport, ease of use, and is already a routine practice for patients with PH. Since this pilot study does not require precise time recording of certain activity (e.g., food intake time and amount), extensive data content entry, and does not extend beyond 6-8 weeks, we plan to use a simple paper and pencil health diary, rather than electronic data capture and to maintain participants' interest and motivation in this data collection with clear expectations and

emphasis of the importance of obtaining this data (Green, Rafaeli, Bolger, Shrout, & Reis, 2006).

Aim 3: To explore the preliminary efficacy of UZIT.

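### The SUS and the final PAHSS and CAMPHOR are collected only at the Week 6 session, with no route for participants who stop earlier, and the retention formula does not define completion

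*Combined protocol and SAP*

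**What the plan says.** **Timing of the final forms.** Table 1 (Measurement / Instrumentation) marks the acceptability survey at Week 6 only, and PAHSS and CAMPHOR at Weeks 1 and 6 only. The Intervention section says "Patients will participate in a total of 6 visits lasting approximately 1 to 1.5 hours per visit to be scheduled within an 8-week period". These are the six UZIT sessions, and no separate assessment visit is listed. The manipulation and enactment checks in the Week 5 column are done at the end of session #5, so the columns appear to follow session numbers.

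**Retention.** Objectives, Aim #1, sets the target at no less than "70% of participants remaining at study completion". Data Analysis, Aim 1, gives the formula: "Retention rate will be calculated as the proportion (completed/enrolled) of participants remaining to study completion". Neither place says what counts as completed.

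**Attendance.** Aim #2 uses a "session completion rate (at least 5 of 6 sessions [83% attendance"]) and applies it to attendance "by the participants retained at the study end". Data Analysis, Aim 2, uses a wider base: "We will compute the number of sessions attended and completed per participant and for the total sample by range, median, mean and mean proportion".

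**Participants who stop.** The only withdrawal provision concerns deletion of their video. Phone calls and texts are described as appointment and practice reminders. No early-termination visit and no mailed or telephoned final form is described.

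**Later use.** Research Design states "We will also explore preliminary efficacy testing to construct sample size estimates for future randomized control trials".

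**The concern.** Under this schedule, ending the sessions also ends the collection of final outcomes. Someone who stops because of illness, travel or dislike of UZIT might still fill in a questionnaire, but nobody is told to ask.

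Two results depend on this. The first is an Aim 2 criterion, a mean SUS above 5: people who left because the programme did not suit them give no score. The second is the Aim 3B change in PAHSS and CAMPHOR, which is analysed with paired tests and so needs the Week 6 form. If those who stop are on average less satisfied or less improved, both results lean towards UZIT, and no choice of test recovers forms that were never requested.

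The undefined word in the retention formula adds a second problem. The same person can be scored as retained or lost, and that choice also decides whether the person enters the attendance standard. A planner of the later trial would want to know separately how many stop the intervention and how many have no outcome. A single retention figure does not show this.

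**Working it through.** **1. The plan's own figures.** Inputs from Sample Size and Statistical Power: two-sided paired t-test, alpha 0.05, standardized mean difference 0.78, final n = 15, enrolled n = 20, attrition 10-15%.

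- Power from the noncentral t with df = n − 1 and noncentrality 0.78 × √n: at n = 15 it is 0.802. The stated power of at least 0.8 reproduces for the t-test.
- Enrolment: 15/(1 − 0.10) = 16.7, so 17; 15/(1 − 0.15) = 17.6, so 18. Enrolling 20 keeps 15 with up to 5 losses (25%).
- Retention target: 0.70 × 20 = 14, so six losses are allowed. This is one below the planned minimum of 15; power at n = 14 is 0.770.

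**2. What one undefined word does.** Let L be the number who leave early and k the number who stop after session 5. L = 3 is 15% of 20. The documents do not give k; the range 0 to 5 is an assumption.

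- If a five-session stopper counts as completed, retention = (20 − L)/20 = 17/20 = 85% for every k.
- If completion needs the Week 6 forms, retention = (20 − L − k)/20.
- Week 1/Week 6 pairs = 20 − L − k on either reading.

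| k | Retention, stopper counted | Retention, stopper not counted | Pairs | Paired-t power at 0.78 |
|---|---|---|---|---|
| 0 | 85% | 85% | 17 | 0.855 |
| 1 | 85% | 80% | 16 | 0.830 |
| 2 | 85% | 75% | 15 | 0.802 |
| 3 | 85% | 70% | 14 | 0.770 |
| 4 | 85% | 65% | 13 | 0.733 |
| 5 | 85% | 60% | 12 | 0.692 |

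The 70% verdict flips at k = 4, and pairs fall below 15 at k = 3. With L = 2 (10%), the verdict flips at k = 5 (13/20 = 65%) and pairs fall below 15 at k = 4 (14 pairs).

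**3. How many might have exactly five sessions.** This needs an attendance probability p, which is also an assumption.

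- Six chances and no rescheduling: 20 × 6p⁵(1 − p) = 7.9, 8.0, 7.1, 4.6 for p = 0.80, 0.85, 0.90, 0.95.
- One slot a week for 8 weeks, so that missed visits can be made up: 20 × 56p⁵(1 − p)³ = 2.9, 1.7, 0.7, 0.1.
- If the Table 1 columns were calendar weeks, only those whose single missed visit is Week 6 would lose the forms. That is one sixth of the first line: 1.3, 1.3, 1.2, 0.8.

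The second line fits the 8-week window best. The spread shows that the count cannot be fixed from the documents.

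**The case against.** The strongest reply is that the plan keeps more than the concern suggests, and most of that reply stands. Attendance is counted per participant and for the total sample, so stopping UZIT is visible. Symptom ratings from sessions 1 to 5 enter the Aim 3A mixed model, which uses all available data. Participants are also debriefed at week 3. Aim 3B is exploratory, and the plan says it will not rely on statistical significance, so the power column above shows scale only.

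A reader might infer several stronger points that the documents do not support:

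- *A five-session stopper meets the attendance standard yet has no outcome.* Aim #2 limits the standard to participants retained at study end. Whether this person is in that group is exactly what is undefined. Someone who misses an earlier week but attends the Week 6 visit has five of six sessions and full final forms.
- *Five to eight of 20 are affected.* That needs six chances with no make-up visits, whereas six visits are spread over an 8-week window.
- *One or two misclassified participants overturn the retention result.* With 2 or 3 early leavers, one or two more makes 3 to 5 losses, still within the six allowed.
- *Only missing outcomes matter for the size of a later trial.* Stopping treatment can also dilute the effect and raise the sample size. The two enter planning differently, but both enter.

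It is also fair to say that judging the 70% target only on forms obtained could let a programme that many people quit pass on mailed questionnaires. That is a reason to report both rates, not to replace one with the other.

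What the reply does not answer is the SUS and the final PAHSS and CAMPHOR. Nothing else in the schedule stands in for them.

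**Conclusion.** The point holds in a limited form. The three end-of-programme instruments are tied to session 6, no route exists for people who stop before it, and completion is undefined in the retention formula. The SUS criterion and the paired Aim 3B change therefore describe those who kept attending. The lean towards UZIT rests on the assumption that people who stop are less satisfied or less improved, which the documents neither state nor test.

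The effect on the retention verdict is modest at the planned 10-15% attrition: four or five further participants would have to stop after session 5 before the reading of completion decided it. The effect on complete pairs comes sooner, at three or four. This does not undermine the study, but it should be changed because forms that were not requested cannot be recovered at analysis.

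**What to change.** 1. Collect the SUS, PAHSS and CAMPHOR at the sixth session or the close of the 8-week window, whichever comes first. Seek them from every enrolled participant who has not refused contact, by mail or phone if needed, and record the mode.
2. Keep the 70% retention target. Report two rates over all enrolled: completed the UZIT programme, with reasons for stopping, and final forms obtained. State which of the two the target uses.
3. State the denominator for the 5-of-6 standard, since Objectives and Data Analysis use different ones.

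The cost is protocol wording, one extra line in the Aim 1 results, and a mailing or call for a few participants. The plan puts the SUS at about 3 minutes and CAMPHOR at about 10, and weekly phone or text contact already exists. The downside is a small number of forms completed by a different mode, which the flag makes visible.

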The study PI will observe and describe any relevant impressions during the UZIT session; and document semi-structured debriefing interviews at the end of the session with patients or therapist independently. Post session debriefing will be conducted with participants at the end of week #3 and week #6 and with interventionist at the end of other sessions (#1, #2, #4, and #5) to ensure adherence to the research protocol. Patients will be asked to rate their preference for each UZIT component ("like" most to least). Exit interview questions will be included at the end of UZIT program.

Home Practice Diary.

Participants will rate the intensity of dyspnea, pain, fatigue, and anxiety and record each UZIT modality used (Table 10). They will describe how they manage other symptoms and the amount of time (minutes) spent each day practicing each component. Participants will be reminded to complete diary entries using paper format prior to each UZIT session.

Pulmonary Arterial Hypertension Symptoms Severity Scale (PAHSS).

PAHSS is specifically designed to assess presence and intensity of 17 common symptoms identified from a sample of PAH patients (Matura et al., 2014), which respondents rate in severity from "0" to "10" (Table 11). This tool demonstrated construct validity with SF-36 ($\alpha = .84$) and the Profile of Mood States ($\alpha = .70$).

Cambridge Pulmonary Outcome Review (CAMPHOR).

CAMPHOR is a 45 item, PH-specific quality of life tool that measures everyday experiences of PH patients. It measures multiple elements of each domain (symptoms, functional activities, and QOL perception) with simple and easy-to-understand phrasing (Table

12). The CAMPHOR demonstrated good internal consistency (Cronbach α = 0.90 – 0.92) and excellent test-retest correlation ($r= 0.86-0.92$) (McKenna et al., 2006), high sensitivity, specificity, and capacity to measure QOL change over time (Meads et al., 2008). Scores within each domain indicate patients' perception of symptoms, functional ability, and QOL. This questionnaire takes approximately 10 minutes to complete.

Modified Borg Dyspnea Scale (MBDS).

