Aim 3A: To explore the preliminary efficacy of weekly UZIT sessions on dyspnea, pain, fatigue, and anxiety. Symptoms of dyspnea, pain, fatigue, and anxiety (symptom intensity) will be assessed in response to each UZIT session. We will plot the weekly visit rating of symptoms (dyspnea, pain, fatigue and anxiety) trajectory pattern from week 1 through week 6 for each participant and by biological variables (e.g. age groups, sex, and NYHA classification). Mixed effect modeling for repeated measures will be used to model the change over time. Estimates derived from mixed effect modeling will be more accurate by accounting for within-subject correlation. It also has the advantage of the most efficient use of data. Estimates are derived from all available data, not just data from completers.

Aim 3B: To explore the preliminary efficacy of 6-week UZIT program on PH-related symptoms and HRQoL. We will compare pre-and post-differences in composite symptoms' presence and severity (PAHSS) and HRQoL (CAMPHOR domains) using McNemar tests for paired proportions and dependent *t*-tests for paired means. As a pilot study to generate information on preliminary efficacy, we will rely on clinical differences. The point estimates and effect sizes from this pilot study will guide the sample size calculation for future larger scale study (efficacy and effectiveness). We will primarily report summary statistics on proportions and 95% confidence intervals at each time point. We will also determine the correlation between changes in PAHSS and CAMPHOR scores with a dose of home practice (minutes/week) to indicate a dose-effect relationship. Furthermore, the frequency and the amount of home practice can serve as an indicator of participants' acceptability of the UZIT program.

IV. Bibliography

Include a reference list of literature cited to support the protocol statement.

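### The stated McNemar power of at least 0.8 at n = 15 is 0.54 to 0.66 on the plan's own inputs, and the binary PAHSS presence outcome is not defined

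*Combined protocol and SAP*

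**What the plan says.** **Sample Size and Statistical Power (section B).** The plan bases its calculation on a "Power analysis using two-sided paired tests", with t-tests for continuous outcomes and McNemar for dichotomous ones. It states that "a sample size of 15 has sufficient power" (at least 0.8) to detect two effects "with a significance level of 0.05":

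- for the t-test, a standardized change of 0.78 or more;
- for McNemar, an "odds ratio of 7 or greater for dichotomous/categorical outcomes, assuming that proportion of discordant pairs is 0.6".

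The 0.6 has no source and is not tied to a named outcome. The same section says small to medium effects will not reach significance and that the pilot will judge by clinical differences instead.

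**PAHSS (section C).** The scale is designed to "assess presence and intensity of 17 common symptoms identified from a sample of PAH patients", each rated 0 to 10.

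**Data Analysis, Aim 3B (section E).** Composite symptom "presence and severity (PAHSS) and HRQoL (CAMPHOR domains) using McNemar tests for paired proportions" are to be compared before and after the programme, and the sentence goes on to name dependent t-tests. It does not say which outcome goes with which test. The main reporting is to be proportions with 95% confidence intervals at each time point. Point estimates and effect sizes are meant to inform the sample size of a later trial.

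**The concern.** There are two linked problems.

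First, one sentence gives the same power for two tests. The continuous half looks right for 15 pairs. The McNemar half looks too generous, because that test uses only the discordant pairs: 60% of 15 is 9 expected pairs, and with so few the exact test in particular is demanding.

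Second, McNemar needs a yes/no variable, and nothing says how 17 ratings become one. The literal binary form of a composite presence is any symptom versus none. In a population selected for functional class II/III, that variable may hardly move.

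What is at stake is the presence part of Hypothesis 3b and the effect size it is meant to hand to the next trial. A reader would also take from the sample size section that dichotomous outcomes are as well powered as continuous ones.

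**Working it through.** **Inputs, all from the sample size section:** n = 15 pairs, two-sided alpha 0.05, standardized mean difference 0.78, odds ratio 7, discordance 0.6.

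**Step 1. Reproduce the continuous half.** Paired t-test, noncentral t, n = 15, effect 0.78: power 0.802. The plan's figure holds.

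**Step 2. Convert the dichotomous inputs.** The proportion improving is 0.6 × 7/8 = 0.525 and the proportion worsening is 0.6 × 1/8 = 0.075, so the net change is d = 0.45.

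**Step 3. Normal approximation (Connor).** Power = Φ[(√n·d − 1.96·√0.6) / √(0.6 − d²)].

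- Numerator: 3.873 × 0.45 − 1.96 × 0.7746 = 1.743 − 1.518 = 0.225.
- Denominator: √(0.6 − 0.2025) = 0.630.
- Power: Φ(0.356) = 0.639.
- Pairs needed for 0.8: (1.518 + 0.8416 × 0.630)² / 0.2025 = 20.7, so 21.

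**Step 4. Full enumeration.** The number of discordant pairs m follows Binomial(15, 0.6). The number improving, given m, follows Binomial(m, 7/8). Power is the total probability of outcomes with p ≤ 0.05.

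| Method, n = 15 | Two-sided | One-sided |
|---|---|---|
| Exact | 0.543 | 0.662 |
| Continuity-corrected | 0.543 | 0.662 |
| Connor | 0.639 | 0.771 |
| Mid-p | 0.659 | 0.766 |
| Miettinen | 0.660 | 0.805 |
| Uncorrected chi-square | 0.663 | 0.813 |

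No two-sided version reaches 0.8. Two of the one-sided versions do.

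**Step 5. How many pairs would be enough, and would planned enrolment supply them?**

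| Pairs | Exact | Mid-p | Uncorrected |
|---|---|---|---|
| 15 | 0.543 | 0.659 | 0.663 |
| 17 | 0.624 | 0.724 | 0.725 |
| 18 | 0.659 | 0.751 | 0.752 |
| 20 | 0.721 | 0.800 | 0.800 |
| 24 | 0.820 | 0.878 | 0.878 |

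The plan enrols 20 and expects 10-15% attrition, leaving 20 × 0.85 = 17 to 20 × 0.90 = 18. That still falls short. Only full retention of all 20 would reach 0.8, and only with the mid-p or uncorrected version.

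**Step 6. The undefined presence variable.** The documents give no PAHSS prevalence or discordance, so everything in this step is assumption.

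*Any of 17 symptoms versus none.* With independent symptoms of equal prevalence p, the chance of at least one is 1 − (1 − p)^17: 0.833 at p = 0.10, 0.977 at p = 0.20, 0.998 at p = 0.30. Positive correlation between symptoms would lower these figures. A discordant patient must be symptom-free at one visit. If prevalence were the same at both visits, discordance could therefore be at most 2 × (1 − 0.977) = 0.046 at p = 0.20, and at most 2 × (1 − 0.833) = 0.334 at p = 0.10.

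*Minimum information.* The two-sided exact test needs at least 6 discordant pairs, all in one direction (2 × 0.5⁶ = 0.031; five give 0.0625). Power at n = 15 and odds ratio 7, by assumed discordance:

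| Discordance | Expected discordant pairs | Exact | Uncorrected |
|---|---|---|---|
| 0.05 | 0.75 | <0.001 | 0.003 |
| 0.10 | 1.5 | 0.001 | 0.032 |
| 0.20 | 3.0 | 0.026 | 0.191 |
| 0.30 | 4.5 | 0.120 | 0.368 |
| 0.50 | 7.5 | 0.416 | 0.575 |
| 0.60 | 9.0 | 0.543 | 0.663 |

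*Other readings.* One McNemar test per symptom, with assumed discordance of 0.3 to 0.5, has exact power 0.12 to 0.42: weak, but it can be answered. A count of symptoms (0-17) analysed by paired t-test has power 0.802 at a standardized change of 0.78.

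**The case against.** The strongest reply is that this is an exploratory aim in a feasibility pilot. The plan says it will judge by clinical differences, reports mainly proportions with intervals, and warns that smaller effects will be missed. The sample of 20 is also set against the size of similar pilots, so little rests on the McNemar figure. That stands as a limit on the consequence. It does not make the power figure right, and it does not help a binary that may be uninformative descriptively as well.

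A reader might go further and infer that McNemar on composite presence would have almost no discordant pairs, so that the presence part of Hypothesis 3b cannot be answered whatever the therapy does. The documents do not support that:

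- Presence is never defined as any symptom versus none. A per-symptom analysis or a count fits the text equally well.
- Paired t-tests stand in the same sentence, and presence is not assigned to McNemar alone.
- No prevalence or discordance is given. High prevalence is inferred from the NYHA II/III criterion and the background statement that PH patients report at least 17 bothersome symptoms. The background also describes symptoms as clustering, so the independence figures in the working are at the upper end for the prevalences assumed.
- The assumed 0.6 is not linked to PAHSS presence, so a low any-symptom discordance does not contradict it.

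Nor does a one-sided calculation coming close to 0.8 show how the plan's figure was obtained. It shows only that the stated two-sided test does not yield it.

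**Conclusion.** The power statement is wrong as written. With n = 15, odds ratio 7, discordance 0.6 and two-sided alpha 0.05, McNemar power is 0.54 to 0.66 depending on the version, not at least 0.8. This rests only on the plan's own inputs. The t-test half of the sentence is correct.

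The presence outcome is under-specified: there is no binary definition and no link to a test. Under the any-symptom reading it would probably be near 100% at both visits. McNemar would then have almost no power (at most 0.001 exact and 0.032 uncorrected for assumed discordance up to 0.10), and the proportions would give the next trial no usable effect size. That part is conditional on the reading and on an inferred prevalence. It does not show that the hypothesis is unanswerable.

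Only exploratory Aim 3b is affected. The feasibility and acceptability aims are not.

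**What to change.** 1. In the sample size section, restate the dichotomous power as about 0.54 to 0.66 at n = 15 under the stated assumptions and name the McNemar version, or delete the claim. Leave the t-test statement as it is.
2. In the Aim 3B analysis, define PAHSS presence as the number of symptoms present (0-17), and report the paired mean change with a 95% confidence interval.
3. Show presence for each symptom as a paired difference in proportions with a 95% confidence interval, labelled descriptive. Intervals at each visit separately do not use the pairing.
4. State which test or estimate belongs to each PAHSS and CAMPHOR outcome.

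The cost is wording only. The data, visits and sample size stay the same. The stated dichotomous power becomes less favourable.
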